#### 5.3.2. Secondary Endpoints

The secondary endpoints for this study include:

- Pharmacodynamic characteristics, including: plasma glucose AUC, Cmax, Tmax and time to reach >70.0 mg/dL will be compared between the treatment groups.
- Symptoms of hypoglycemia (if present) as documented using the hypoglycemia symptom questionnaire ([Appendix 1](#)) which is completed every time blood is sampled for determination of plasma glucose during the hypoglycemia induction procedure, at baseline immediately before injection and every 5 minutes until 45 minutes following administration of glucagon.
- Pharmacokinetic parameters include: descriptive analysis of AUC, Cmax and Tmax of the different ethnicities.

- Safety-related parameters including:
  - Vital signs
  - Physical exam
  - ECG
  - Standard safety laboratory parameters
  - Incidence of adverse events (AEs) and serious adverse events (SAEs)
  - Subjective injection site discomfort as reported by subjects using a 100-mm VAS and other questionnaires ([Appendix 2](#))
  - Erythema and/or edema formation at site of injection assessed by an investigator using the modified Draize scale (see [Appendix 3](#))

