**Table 3: Randomized treatment sequence**

Group	Dose 1	Dose 2
1	G-Pen™ 1 mg	Lilly 1 mg
2	Lilly 1 mg	G-Pen™ 1 mg

The procedure to evaluate the efficacy of the G-Pen™ (glucagon injection) consists essentially of inducing hypoglycemia by IV administration of regular insulin diluted in normal saline. Each participant will undergo two episodes of insulin-induced hypoglycemia in random order and receive 1 mg G-Pen™ (glucagon injection) during one episode and 1 mg Lilly Glucagon during the other episode. A combination of one or more IV bolus doses of insulin along an IV infusion of insulin will be used to decrease a subject's plasma glucose to a target <50.0 mg/dL. The IV insulin infusion will be stopped once the plasma glucose is <50.0 mg/dL. As per Section 11.2, all plasma glucose levels will be based on the average of two readings taken at each time point.

After a confirmatory plasma glucose of <50.0 mg/dL is obtained at least 5 minutes after the initial reading < 50.0 mg/dL, the subject will be treated subcutaneously in the upper arm, leg or abdomen with either 1 mg Lilly Glucagon or 1 mg G-Pen™ (glucagon injection).

Blood glucose levels will be monitored for 90 minutes post-dosing. It is believed that blood glucose <50 mg/dL will be low enough to generate neuroglycopenic and autonomic symptoms in most subjects, yet high enough to avoid impairment of consciousness. Consequently, subjects will complete a questionnaire about symptoms of hypoglycemia [Nermoen] during the hypoglycemia induction phase, and for 45 minutes after treatment with glucagon.

After a wash-out period of 7 to 28 days, subjects will return to the clinic and the procedure will be repeated with each subject crossed over to the other treatment.

After study-related procedures are performed on each of the treatment days, subjects will be discharged after receiving a meal as per each site's usual practice. A follow-up visit as a safety check will be conducted 3-14 days following administration of the final dose.

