Note: If consecutive readings of plasma glucose < 50.0 mg/dL are not achieved within 3 hours of the start of the hypoglycemia induction phase, the visit should be terminated. In this case:

- i. Study drug should NOT be given.
- ii. The visit should be terminated and rescheduled after a 7-day minimum wash-out period.
- iii. If appropriate, insulin pump therapy should be restarted and a meal provided. The subject can leave the clinic after plasma glucose is confirmed to be between 70 and 180 mg/dL.
- h. Following study drug administration, plasma glucose will be measured every  $5 \pm 2$  minutes until 90 minutes post-dosing. Note: At their discretion, investigators may continue to monitor glucose levels for safety during the remainder of the visit.
  - i. At any time post-dosing if a subject exhibits signs of coma or convulsions, or if plasma glucose remains < 60.0 mg/dL at 30 minutes post-dosing, a 25 mL IV bolus dose of 50% dextrose will be given. Signs and symptoms should be monitored and if the subject's condition fails to improve within 15 minutes, additional dextrose or other intervention may be given at the discretion of the investigator.
  - j. Additional blood samples will be collected at 10, 20, 30, 45, 60, 90, 120, 180 and 240 minutes post-dosing with  $\pm$  5 minutes per collection, and processed and stored at -70C for determination of plasma glucagon and potentially insulin levels (see Table 5).
  - k. At 240 minutes post-dosing, the subject will resume pump therapy, if applicable, and will be given a meal. The subject can then leave the clinic after plasma glucose is confirmed to be between 70 and 180 mg/dL. Note: If necessitated by rising glucose levels, insulin pump therapy can be re-started as early as 120 minutes post-dosing. Additionally, IV insulin can be administered to non-pump using subjects to prevent hyperglycemia, starting at 120 minutes post-dosing with glucagon.

8. Subjects will complete a questionnaire regarding severity of hypoglycemia symptoms ([Appendix 1](#)) at various time points, including:
  - a. Just before the IV bolus push dose of insulin is given at the start of the hypoglycemia induction procedure.
  - b. Every time blood is drawn for evaluation of plasma glucose concentration during the induction procedure.
  - c. Just before study drug is administered, and

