#### **10.2.2. Visit 3 - Treatment 2 (Day 7-28)**

The subject will return 7 to 28 days following the first treatment visit. The procedures to be followed at this visit are as listed in [Section 10.2.1](#), with the exception of items #4 as no blood work is required at Visit 3. At this visit, the other study medication will be given, so that between the two dosing visits, each subject will have received G-Pen™ (glucagon injection) once and Lilly Glucagon once.

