#### **13.2.2. Pharmacodynamic Secondary Endpoints:**

Time for plasma glucose to reach >70.0 mg/dL, AUC,  $C_{max}$  and  $T_{max}$  will be compared between the treatment groups using a mixed model with treatment, period and sequence as terms.

Symptom relief will be analyzed as aggregate scores for the four autonomic, four neuroglycopenic symptoms and 8 total symptoms (see [Appendix 1](#)). The time to the minimal score post baseline will be described and compared between the treatment groups using a mixed model with treatment, period and sequence as terms. Similarly, the time to first reporting of “no” for the global hypoglycemia question will be described and compared between the groups.

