## APPENDICES

### APPENDIX 1. HYPOGLYCEMIA SYMPTOM QUESTIONNAIRE

*Investigative Site Instructions:* The subject should complete the Hypoglycemia Symptom Questionnaire at the following time points:

- Just before the IV bolus push dose of insulin is given at the start of the hypoglycemia induction procedure.
- Every time blood is drawn for evaluation of plasma glucose concentration during the induction procedure.
- Just before study drug is administered.
- Every 5±2 minutes after glucagon is administered, until all symptoms have abated (i.e., all symptoms have score = 1) or 45 minutes post-dosing, whichever occurs first.

*Note:* If a subject is unable to physically complete the questionnaire, the subject will provide verbal responses, which will be recorded on the questionnaire by study staff. Documentation will be provided on each completed questionnaire as to who completed the form.

*Subject Instructions:* Please rate the current intensity (severity) of each of the following symptoms on a scale of 1-6, with a minimum score of “1” meaning the symptom was absent and a maximum score of “6” meaning the symptom was severe. For the final question, please answer “yes” or “no.”

Neuroglycopenic Symptoms	Severity Score (1-6)
Dizziness	
Blurred vision	
Difficulty in thinking	
Faintness	
Autonomic Symptoms	Severity Score (1-6)
Sweating	
Tremor	
Palpitations	
Feeling of nervousness	
Overall Assessment of Hypoglycemia	Yes/No
Do you currently feel hypoglycemic?	

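### The symptom-relief model in Section 13.2.2 leaves out the pre-dose symptom score that is collected at both visits; the analysis is valid, but may be less precise than the data allow

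*Combined protocol and SAP*

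**What the plan says.** Section 13.2.2 defines the endpoint: "Symptom relief will be analyzed as aggregate scores for the four autonomic, four neuroglycopenic symptoms and 8 total symptoms". The time to the minimal score after baseline is then to be described and "compared between the treatment groups using a mixed model with treatment, period and sequence as terms". No baseline term is listed and no change from baseline is used. The phrase about being after baseline only fixes the window in which the minimum is sought.

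The starting value is collected. Section 5.3.2 has the questionnaire completed "at baseline immediately before injection and every 5 minutes until 45 minutes following administration of glucagon". Appendix 1 lists a completion "Just before study drug is administered", as does item 8c of Section 10.2.1. For the second treatment visit, Section 10.2.2 states "The procedures to be followed at this visit are as listed in" Section 10.2.1, with only the item 4 blood work dropped. Each subject who completes both visits therefore has two pre-dose scores on each of the three scales.

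The last sentence of Section 13.5 leaves further detail on Sections 13.1 to 13.5 to the SAP.

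**The concern.** In a two-period crossover each subject is their own control, so stable differences in symptom intensity cancel. A difference between the two visits in how symptomatic the same subject is at dosing does not cancel. It stays in the residual of the within-subject comparison.

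The plan leaves room for such differences. Dosing is triggered by two consecutive glucose readings below 50.0 mg/dL, not by symptoms. The insulin bolus is calculated from that day's starting glucose, with investigator discretion. The infusion may be restarted, and induction may last up to 3 hours (Section 10.2.1). Section 7.1 expects the glucose level reached to be "low enough to generate neuroglycopenic and autonomic symptoms in most subjects", so not in all.

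A link between starting score and time to the minimum is plausible. Each item has a floor of 1 (Appendix 1), and collection stops once every item is at 1 or at 45 minutes. A subject who starts near the floor has little distance to fall. If the link is real, the planned model gives a wider confidence interval for the symptom comparison than the same data could give.

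**Working it through.** **The plan's own figure.** The documents give no power, variance or correlation for the symptom analysis. The only power statement is for the primary criterion: over 90% with 75 subjects (Section 13.1.2). Simulating the 3x3 table described there (scores 0, 1, 0.2 and 0.1; acceptance if the mean plus 2.6 SE is at most 0.1; 100,000 replicates per scenario) gave a lowest power of 0.908 with equal failure rates. That was at 5% total failure, 1% in each discordant cell and 15% missing per treatment. The statement reproduces. It does not bear on the symptom model.

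**Inputs for the symptom model.**
- From the plan: 75 subjects; treatment, period and sequence as terms; a pre-dose score at each visit.
- Assumed: two-sided 5% test; an effect with 80% power unadjusted; ρ, the correlation between the within-subject difference in pre-dose score and the within-subject difference in time to minimum.

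**Formulae.**
- Variance of the treatment contrast after adjustment, relative to before: 1 − ρ².
- Adjusted power: Φ[(1.96 + 0.8416)/√(1 − ρ²) − 1.96].
- Cost of estimating the slope: multiply the variance by 72/71, that is 1 + 1/71.
- Unadjusted sample size with the same precision: 75/(1 − ρ²).

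Example, ρ = 0.5: √0.75 = 0.866; 2.8016/0.866 = 3.235; 3.235 − 1.96 = 1.275; Φ(1.275) = 0.899.

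| ρ | 1 − ρ² | SE ratio | Power | Power after slope cost | Equivalent N |
|---|---|---|---|---|---|
| 0 | 1.00 | 1.000 | 80.0% | 79.4% | 75.0 |
| 0.1 | 0.99 | 0.995 | 80.4% | 79.8% | 75.8 |
| 0.2 | 0.96 | 0.980 | 81.6% | 81.0% | 78.1 |
| 0.3 | 0.91 | 0.954 | 83.6% | 83.1% | 82.4 |
| 0.4 | 0.84 | 0.917 | 86.4% | 85.9% | 89.3 |
| 0.5 | 0.75 | 0.866 | 89.9% | 89.5% | 100.0 |
| 0.7 | 0.51 | 0.714 | 97.5% | 97.4% | 147.1 |

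**Check for bias.** A simulation of the crossover on period differences (38 and 37 subjects per sequence, 3,000 replicates, normal errors) compared the two models.
- At ρ = 0.5 the mean estimates were 0.3245 unadjusted and 0.3242 adjusted, against a true effect of 2.8016/√75 = 0.3235. The SE fell from 0.113 to 0.100.
- At ρ = 0.7 the SE fell from 0.118 to 0.084. At ρ = 0.1 it was essentially unchanged (0.113 and 0.114).
- Rejection under no effect was 0.044 to 0.058 unadjusted and 0.046 to 0.063 adjusted. The Monte Carlo SE is √(0.05 × 0.95/3,000) = 0.004. Both tests are exact under these conditions, and the high values came from the same run for both models, so they are simulation noise.

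**How large might ρ be?** Two illustrative simulations built the endpoint from assumed symptom decay on the 5-minute grid with the 45-minute cap. One gave ρ from 0.17 to 0.53 and power gains of 0.3 to 14 points. The other used eight integer items with reporting noise and gave ρ from 0.08 to 0.52; only 7 of 36 settings exceeded 0.35, all at the lowest noise. Neither rests on trial data. They show only that the gain can run from negligible to material.

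**The case against.** **Nothing is wrong with the planned model.** True. Treatment, period and sequence make a standard crossover model. A reader might infer that a chance difference in pre-dose severity biases the treatment estimate. The documents do not support that: sequence is randomised, chance differences average out over about 75 pairs, and the planned standard error already reflects them. The loss is one of precision.

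**The SAP may add the covariate.** Section 13.5 defers detail, and no separate SAP text is in the document reviewed. The point therefore concerns the model as written. But Section 13.2.2 goes as far as naming the terms, and baseline is not among them, so the deferral does not settle the matter.

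**The benefit is unproven.** This stands. The endpoint is time to the subject's own minimum, not to a fixed threshold. With noisy integer scores, a subject who does not fully recover can reach the minimum at almost any time, which weakens the link with the starting score. Both visits also use the same subject, the same induction rules and the same glucose trigger, so much of the variation in severity may be stable and already removed. A gain of 5 points needs ρ of about 0.35, and nothing in the documents shows that it is that high.

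**Little rests on it.** Also fair. The objective is to describe and compare symptom relief, with no stated hypothesis or power.

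**The covariate does not solve everything.** Visits without symptoms at dosing, scores at the floor and the 45-minute cap still need their own rules. That limits what the change achieves but is no reason to leave the score out.

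**Conclusion.** The concern holds as an optional gain in precision. Section 13.2.2 omits a pre-dose score that the trial collects at both visits. The planned analysis is valid without it.

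The size cannot be derived from the documents. Before the slope cost, and assuming 80% unadjusted power, the gain is at most about 2 points for ρ of 0.1 to 0.2, about 4 at 0.3 and about 10 at 0.5. At ρ = 0 adjustment loses about 0.6 points, and at 0.1 the slope cost cancels the gain. The possible loss is under one point and the possible gain is several, which favours adjustment without showing that it is needed.

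A reader might also infer that the trial's conclusion or sample size is at risk. Neither is. Acceptance rests on the primary criterion in Section 13.1.1, which does not use the symptom scores.

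**What to change.** In Section 13.2.2, and in the SAP to which Section 13.5 defers, state before unblinding that each model for time to minimal symptom score includes the pre-dose aggregate score of the same scale (autonomic, neuroglycopenic or total). Enter it as two terms, the subject's mean over the two visits and the visit's deviation from that mean, so that the treatment contrast is adjusted with the within-subject slope. Report the model with treatment, period and sequence only as a sensitivity analysis.

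The covariate is measured before each visit's dose, with subject and investigator blinded (Section 9.2). Visits are 7 to 28 days apart and glucagon is described as very short-acting (Section 6.4), so the second pre-dose score is unlikely to carry an effect of the first treatment.

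The cost is a line of wording and 1 to 2 degrees of freedom. No new data, visits or subjects are needed. The timing matters: a covariate added after unblinding would look chosen from the data.

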### 5.2. Secondary Objectives

The secondary objectives of this study are:

- To compare the pharmacodynamic characteristics of G-Pen™ (glucagon injection) 1 mg (test) versus Lilly Glucagon (glucagon for injection [rDNA origin]) 1 mg (reference) in T1D patients who are in a state of insulin-induced hypoglycemia,
- To describe and compare hypoglycemia symptom relief of the two treatments,
- To describe G-Pen™ (glucagon injection) 1 mg pharmacokinetics in the major ethnicities and races in the US: non-Hispanic Whites, Hispanics, and African-Americans; and
- To compare the safety and tolerability of G-Pen™ (glucagon injection) 1 mg (test) versus Lilly Glucagon (glucagon for injection [rDNA origin]) 1 mg (reference) in T1D patients who are in a state of insulin-induced hypoglycemia.

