  - d. Every 5±2 minutes after glucagon is administered until all symptoms have abated (i.e., all symptoms have score = 1) or 45 minutes post-dosing, whichever occurs first.
9. Local tolerability will be assessed as follows:
  - a. Subjects will complete a Visual Analog (VAS) questionnaire regarding injection site discomfort ([Appendix 2](#)) at 10±5 and 30±5 minutes post-dosing, and again at 240±5 minutes post-dosing if VAS score reported at 30 minutes is > 0 mm.
  - b. Subjects will complete an Injection Site Discomfort Description and Duration Questionnaire at 10±5 minutes post-dosing. If discomfort is ongoing at 10 minutes post-dosing, the questionnaire will be updated before the subject leaves the clinic to document the final duration.
  - c. An investigator will use the modified Draize scales ([Appendix 3](#)) to assess erythema and edema formation at the injection site at 10±5 and 30±5 minutes following administration. Any injection site with a score > 0 for either erythema or edema at 30 minutes post-dosing will be re-evaluated for both at 240±5 minutes post-dosing. If any scores remain > 1 at the 240-minute evaluation, the subject may leave the clinic but will be instructed to contact study staff if the condition fails to resolve.
10. Adverse events reported by the subject or observed by an investigator will be recorded in the CRF.

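### The symptom-relief time in Section 13.2.2 does not define the minimal score and has no rule for sessions unresolved at 45 minutes, so it can understate or hide a difference in resolution

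*Combined protocol and SAP*

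**What the plan says.** Section 5.2 lists as a secondary objective: "To describe and compare hypoglycemia symptom relief of the two treatments". Section 13.2.2 gives the analysis: "Symptom relief will be analyzed as aggregate scores for the four autonomic, four neuroglycopenic symptoms and 8 total symptoms", with a pointer to Appendix 1. It then says: "The time to the minimal score post baseline will be described and compared between the treatment groups using a mixed model", the terms being treatment, period and sequence. Time to the first negative answer to the global question ("Do you currently feel hypoglycemic") is to be compared similarly. Time to plasma glucose above 70.0 mg/dL is analysed with the same mixed model.

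Appendix 1 scores each of eight symptoms from 1 to 6, "with a minimum score of “1” meaning the symptom was absent". Section 10.2.1, item 8d, and Appendix 1 have the post-dose questionnaire repeated every 5 minutes "until all symptoms have abated (i.e., all symptoms have score = 1) or 45 minutes post-dosing, whichever occurs first". Section 5.3.2 has it every 5 minutes to 45 minutes and mentions no early stop.

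Two places allow for sessions with few or no symptoms before dosing. Section 5.3.2 reads "Symptoms of hypoglycemia (if present) as documented using the hypoglycemia symptom questionnaire", and Section 7.1 expects that glucose below 50 mg/dL "will be low enough to generate neuroglycopenic and autonomic symptoms in most subjects". Section 10.2.1, item 7, provides for IV dextrose in some sessions, which can fall inside the symptom window. Section 13.5 leaves further detail of the analyses to an SAP; the document supplied for review contains no such text.

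**The concern.** The endpoint and the model are already fixed in Section 13.2.2, but the term that defines the endpoint is not, and a mixed model of observed times has no natural place for a session that never reaches the event.

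- **Own lowest score.** Every session has a value, but it measures when improvement stopped, not whether symptoms went away. A total score that falls from 20 to 18 at 5 minutes and improves no further scores 5 minutes. A session that clears fully at 25 minutes scores 25. The worse outcome looks faster.
- **Scale floor.** A session above the floor at 45 minutes has no time. If it is dropped, only resolvers are compared. If it is given 45 minutes, it counts as just resolved.

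At stake is a stated secondary objective. A product that leaves more subjects symptomatic could show no difference in relief time, or too small a one. The choice between readings would also stay open until the data are seen. Time to first *no* and time to above 70.0 mg/dL likewise lack a rule for sessions that never reach the event, or reach it only after dextrose.

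**Working it through.** The plan gives no sample size, effect, variance or resolution rate for this endpoint, so there is no figure to reproduce. The check is one identity with assumed inputs, backed by simulation.

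**From the documents.** Eight items scored 1 to 6 give a total from 8 to 48 and a floor of 4 for each four-item subscale. Readings are every 5 minutes to 45 minutes. There are 75 crossover subjects (Section 9.1).

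**Assumed.** By 45 minutes 95% of Lilly and 80% of G-Pen sessions resolve, and resolvers are equally fast on both. The observed mean time in resolvers, *m*, is 13.5, 23.0 or 30.9 minutes (nominal 10, 20, 28). Unresolved sessions reach their own lowest score at a mean of 13.2 minutes (early plateau) or 38.6 minutes (slow decline), with score noise of ±1 point.

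**Formula.** If an unresolved session is given the value *v*, and *p* is the proportion resolving, the mean difference, G-Pen minus Lilly, is

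(p_Lilly − p_G-Pen) × (v − m) = 0.15 × (v − m).

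If unresolved sessions are dropped, the difference is m − m = 0.

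| Handling | m = 13.5 | m = 23.0 | m = 30.9 |
|---|---|---|---|
| Own lowest, early plateau (v = 13.2) | 0.15 × (−0.3) = −0.05 | 0.15 × (−9.8) = −1.47 | 0.15 × (−17.7) = −2.66 |
| Own lowest, slow decline (v = 38.6) | 0.15 × 25.1 = +3.77 | 0.15 × 15.6 = +2.34 | 0.15 × 7.7 = +1.16 |
| Floor, unresolved dropped | 0 | 0 | 0 |
| Floor, unresolved set to 45 | 0.15 × 31.5 = +4.73 | 0.15 × 22.0 = +3.30 | 0.15 × 14.1 = +2.12 |

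If unresolved sessions truly cleared at 90 minutes, the difference at m = 23.0 would be 0.15 × 67.0 = +10.05 minutes. Setting them to 45 therefore shows about a third of it, with the right sign.

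**Simulation.** There were 2,000 trials per scenario, analysed with a REML mixed model with treatment, period, sequence and random subject. The figures below are for the three values of *m* in order.

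- Own lowest, early plateau: −0.01 / −1.48 / −2.63 minutes; significant in favour of the worse product in 3% / 27% / 51% of trials.
- Own lowest, slow decline: +3.82 / +2.39 / +1.12 minutes; significant in the right direction in 73% / 51% / 19%.
- Floor, dropped: about 0.0 minutes throughout; significant in 4.2–5.6%, which is chance.
- Floor, set to 45 (crossover t-test, two runs): right direction in 80–84% / 72% / 51–52%.
- Unresolved counted as not achieved: paired log-rank scores 77% in the right direction in all three; paired ranks 49–50%.

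A second simulation, with independent sessions and paired t-tests (resolver mean 20 minutes, plateau mean 10), agreed: own lowest −1.5 minutes, wrong direction in 23%; dropped 0.0 minutes, 5%; set to 45, +3.3 minutes, 58%. Comparing the proportion resolved (exact McNemar test) detected the deficit in about 75%.

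**Sensitivity.**

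- *Score noise.* For m = 23.0 / 30.9, wrong-direction significance under the early plateau was 64% / 75% with no noise, 26% / 52% at ±1 point (t-test run), 6–8% / 26–28% at ±3 and 4% / 21% at ±5.
- *Smaller deficit (90% against 95%).* At m = 23.0, own lowest with early plateau gives 0.05 × (−9.8) = −0.49 minutes. Wrong-direction significance is 2% / 6% / 11% across the three values of *m*. Paired log-rank scores detect the deficit in only 16%, and paired ranks in 9%.
- *Equal resolution.* The first factor is zero, so every handling gives about 0.

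**Glucose time.** Section 13.1.1 expects failures below 5%, and Section 13.1 defines failure over 0 to 30 minutes. Sessions never above 70.0 mg/dL by 90 minutes are therefore at most a subset of those. Assume 5% against 1% failing and a mean of 12 minutes otherwise. If none of the failures ever reaches 70.0, holding them at 90 minutes gives 0.04 × (90 − 12) = 3.1 minutes (3.0 simulated on the 5-minute grid), against 0.0 if they are dropped. That is an upper bound, with no reversal.

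**The case against.** Five points can fairly be made for the plan.

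1. *The floor is the natural reading.* Section 13.2.2 points to Appendix 1, which calls an item score of 1 the minimum, and Section 10.2.1 defines abatement as every item at 1. This stands, and makes own lowest the less supported reading. It does not define the aggregate endpoint, and it leaves unresolved sessions without a rule.
2. *Dropping is only one option.* Assigning 45 minutes fits the planned model and, in the example, detects the deficit about as well as log-rank scores for fast or middling resolvers. This also stands. Hiding the difference depends on dropping; understating the minutes does not.
3. *The assumed rates have no anchor.* True. Nothing in the documents suggests that 20% of sessions would still be symptomatic at 45 minutes.
4. *Other analyses help.* Aggregate scores and time to first *no* would partly show persisting symptoms, but time to first *no* has the same gap.
5. *The SAP may settle it.* It may. But Section 13.2.2 already names an endpoint and an uncensored model, so a censoring rule would change a stated method as well as add detail.

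A reader might infer that the analysis will favour the worse product. The documents do not support that: reversal needs the less favoured reading, an early plateau, slower resolvers and little score noise. A reader might also infer that a session already at the floor before dosing counts as 5 minutes. No section gives it a value, and under the early stop it might have no post-dose questionnaire. Nor is it settled that collection stops while a subject still answers *yes* to the global question: Section 10.2.1 and Appendix 1 allow it, but Section 5.3.2 has no early stop.

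**Conclusion.** The point holds as a gap in definition and in handling. As written, an unresolved session may be scored as fast, left out, or capped at 45 minutes, and each choice gives a different answer from the same data. In the worked example at m = 23.0, one 15-point deficit in resolution appears as −1.5, 0.0 or +3.3 minutes.

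The size rests wholly on assumed resolution rates, plateau times and score noise. All these shifts are smaller than the 5-minute sampling interval, and they vanish if nearly all sessions resolve on both products. The effect on glucose time is small. The primary non-inferiority decision is untouched. This is a cheap improvement to a secondary analysis. The documents do not support reading it as a threat to the trial's conclusion, or as a reason to require one particular test.

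**What to change.** Before unblinding, in Section 13.2.2 and the SAP:

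1. Define symptom relief as time to first reaching the floor, with all items in the aggregate equal to 1.
2. Count sessions not at the floor by the end of collection as not achieved. Either censor them at 45 minutes in a time-to-event or rank analysis that respects the crossover pairing, or set them to 45 minutes or the worst rank. Never drop them. Report the number and proportion unresolved by product.
3. Report by product how many sessions were already at the floor before dosing, with a sensitivity analysis that excludes them.
4. Apply the same rule to time to first *no* and to time to above 70.0 mg/dL (cap 90 minutes), counting sessions given dextrose before the event as not achieved.
5. Reconcile Section 5.3.2 (questionnaire to 45 minutes) with the early stop in Section 10.2.1, item 8d, and Appendix 1.

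Cost: wording and a little more analysis, with no new visits or samples. The summary is slightly less simple than a mean difference in minutes.

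Two cautions on method. Excluding pre-dose floor sessions belongs in the sensitivity analysis: if 20% of sessions were at the floor, 0.8 × 0.8 × 75 = 48 pairs would stay complete, and the log-rank score test would fall from 77% to 55% in the example. Any time-to-event method should have its type 1 error checked by simulation: a marginal Cox fit with cluster-robust variance rejected in 12–14% of trials with no true difference.
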